### 8.3.4 Secondary Endpoint- Incidence of all SCA events

Descriptive statistics will be used to analyze the incidence and etiology of SCA from the beginning of LifeVest use to end of study. "Sudden Cardiac Death" will be defined as an unexpected, non-traumatic, non-self-inflicted fatality in otherwise stable subjects who die within one hour of the onset of the terminal symptoms. Subjects dying more than one hour after a sudden cardiac arrest (SCA) from a ventricular arrhythmia will be designed as non-sudden death due to ventricular arrhythmia. For unwitnessed deaths participants will meet the definition of sudden cardiac death if they are found dead within 24 hours of being well, assuming there is no evidence of another cause of death during that time period. Autopsy results may be used when available.

8.3.5 Secondary Endpoint- Incidence and etiology of other WCD recorded arrhythmias, such as asystole and sustained (≥ 30 seconds) supra-ventricular arrhythmias.

Descriptive statistics will be used to analyze the incidence of non-VT/VF events that are recorded by the WCD. Such arrhythmic events will be evaluated for correlation with the other endpoints. ECG recordings will be adjudicated by a committee independent of the sponsor.

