<sup>13 Roth et al, "Use of Guideline-Directed Medications for Heart Failure Before Cardioverter-Defibrillator Implantation," JACC 2016; 67:1062-9.

patients with EF  $\leq$ 40%. They found that 40% of patients had an EF $\geq$ 45% at 6 months, and 25% had an EF $\geq$ 50% . Among DEFINITE trial subjects with follow-up EF measurements, 32% improved EF over 35% during the first two years of the trial despite enrollment criteria of EF  $\leq$ 35% and "stable" HF for at least 30 days . They also found that patients with LVEF improvement had a decreased risk of total mortality, although no reduction in arrhythmic events. In contrast to the IMAC-2 study, the DEFINITE study excluded reversible cardiomyopathies, which may explain the lower recovery rate seen in DEFINITE patients.

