## 2 Study Objectives

## 2.1 Primary Objective(s)

The primary objective of this study is to observe the rate of recovery of ventricular function (EF>35%) between 90 and 180 days in newly diagnosed HF with reduced EF patients who were prescribed the WCD while being initiated on their HF medications. This will be measured from EF closest to before hospital discharge, then at 90, 180 and 360-days after WCD start, regardless of continued WCD use, prior EF improvement, or ICD implantation. While approximately one-third of the patients will likely experience EF recovery in the first 90 days, we hypothesize that an additional 5-10% of patients will experience EF improvement between 90 and 180 days as GDMT is achieved. This would be considered clinically significant in terms of the potentially avoided ICD implantations. Outcomes will be tracked and reported for three pre-specified groups based on assessment of SCD risk at 90 days of WCD use:

- 1) Patient improved (EF >35%), SCD risk deemed to be negligible. These patients are expected to end WCD use and not receive an ICD.
- 2) Patient improved EF from start of WCD use (a positive change of at least 5 percentage points in EF), or has a borderline EF of 30-35%, but still has continued SCD risk (EF ≤ 35%). These patients are expected to continue to use the WCD for an additional 3 months.
- 3) Patient not improved from start of WCD use (no change or worsening of EF), EF<30% and has continued high SCD risk. Those on GDMT are expected to be evaluated for an ICD. Those not yet on GDMT may continue the WCD for an additional 90 days.

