## 2.2 Secondary Objective(s)

The specific secondary objectives are to:

2.2.1 Observe the incidence and etiology of SCA and all sustained VT/VF arrhythmias during WCD use.

- 2.2.2 Observe the incidence of other arrhythmias during WCD use, such as asystole and supra-ventricular arrhythmias that are recorded by the device.
- 2.2.3 Collect ICD treatment data for those who receive an ICD, and evaluate for appropriateness.
- 2.2.4 Observe the effectiveness of the wearable defibrillator worn by this population in treating ventricular arrhythmias. Clinical outcomes data from any defibrillation or cardiac event will be collected, including device data on appropriate arrhythmia detection and shock delivery.
- 2.2.5 Evaluate the effect of wearable defibrillators on 90,180, 270, and 360-day mortality following WCD start in HF patients. Assessment of survival will be made at these time points for those entered into the study. A mortality review will be conducted to group all deaths as cardiac or non-cardiac, and sudden or non-sudden.
- 2.2.6 Collect economic and healthcare utilization data on all patients.

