## 3.3 Secondary Study Endpoints

The secondary endpoints are observational and include documentation of any SCA/SCDs, including any treatments by the WCD or ICD, any untreated sustained ventricular arrhythmias that are recorded by the WCD, and the mortality following discharge in HF patients. We will also collect economic and healthcare utilization data on all patients.

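### One SCA incidence to end of study mixes risk with detection and treatment, because finding non-fatal events depends on whether the patient still has a device

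*Combined protocol and SAP*

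**What the plan says.** Two sections set different windows for the same endpoint. Objective 2.2.1 is to "Observe the incidence and etiology of SCA and all sustained VT/VF arrhythmias during WCD use". The analysis in 8.3.4 is to "analyze the incidence and etiology of SCA from the beginning of LifeVest use to end of study", a window that does not depend on the device.

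The endpoint is broad. Section 3.3 describes it as "documentation of any SCA/SCDs, including any treatments by the WCD or ICD", and 3.3.1.4 counts anti-tachycardia pacing as well as shocks as treatment. SCD is defined in 3.3.1.1 and again in 8.3.4. SCA itself is defined in neither place.

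Section 2.1 states: "Outcomes will be tracked and reported for three pre-specified groups based on assessment of SCD risk at 90 days of WCD use". The first group is "Patient improved (EF >35%), SCD risk deemed to be negligible", with the expectation: "These patients are expected to end WCD use and not receive an ICD". The second group is expected to continue the WCD. The third is expected to be evaluated for an ICD or may continue the WCD.

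Arrhythmia capture is tied to the device. A sustained ventricular arrhythmia exists by definition only as a WCD recording (3.3.1.3). The sponsor's notice to sites is triggered by a WCD recording (6.3.1.1). Arrhythmia adjudication covers shocks and ECG recordings (7.2, 8.3.2, 8.3.3).

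**The concern.** After day 90 the same arrhythmia has different chances of becoming a study event. In a patient wearing a WCD or carrying an ICD, it can be recorded, treated, notified and adjudicated. In a patient with neither, it becomes known only if it ends in death or in an arrest that someone recognises. Because device status is expected to follow the day-90 group, a table of SCA incidence by group would compare detection and treatment as well as risk.

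At stake is the reading of a low count in patients whose EF recovered. It could be taken to show that their arrhythmic risk is low once the device is off. The planned data cannot show that unless events are separated by how they were found. The plan has no monitored-time denominator and no reporting by source of ascertainment, although daily wear time is recorded (7.1).

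**Working it through.** **1. What is collected with and without a device**

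| Event | On WCD or ICD | Off device | Source |
|---|---|---|---|
| Death, vital status | yes | yes | 6.4, 8.3.6 |
| SCD, including unwitnessed | yes | yes, no recording needed | 3.3.1.1, 8.3.4 |
| Clinically recognised arrest | yes | yes, asked at each contact | 6.2, Table 2 |
| Shock or pacing therapy | yes | cannot occur | 3.3.1.4, Table 2 |
| Untreated sustained VT/VF | WCD only | no | 3.3.1.3, 8.3.3 |
| ECG evidence of etiology | largely device recordings | largely lost | 7.2, 8.3.2 |

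The first three rows do not need a device. The last three do.

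**2. Direction of the bias**

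- Missed self-terminating or unrecognised episodes lower the off-device count.
- A shock or pacing for an episode that would have stopped by itself raises the on-device count.
- A shock that prevents a death lowers the on-device count of SCD.

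These effects do not all point the same way, so a pooled count has no predictable sign of bias.

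**3. Follow-up without device recording**

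Follow-up is 12 months from WCD start (3.1.3), taken as 360 days.

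- WCD stopped at day 90, no ICD: (360 − 90)/360 = 270/360 = 75%.
- WCD stopped at day 180, no ICD: (360 − 180)/360 = 180/360 = 50%.

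The second line shows that unmonitored time is not confined to the recovered group. Patients with EF ≤ 35% who refuse a WCD or ICD also stay in follow-up (3.1.5, 5.4.1).

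**4. The plan's own event figure**

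Section 8.1.1 assumes a 1.5% shock rate in the extended-wear group. The binomial probability of two or more events is 1 − (1 − r)^N − N·r·(1 − r)^(N−1).

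- N = 200, r = 0.015: 0.803 (stated about 80%).
- N = 250, r = 0.015: 0.890 (stated as more than 90%, so about one point short).

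The figure is reproduced closely enough to serve as a scale for event numbers.

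**5. How few events there would be (illustration, not an estimate)**

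The plan expects that "approximately one-third of the patients will likely experience EF recovery in the first 90 days". One third of the 738 patients with a day-90 EF (8.1) is 246. One third of the current study cap of 600 (5.2) is 200. Assume that the 1.5% rate also applies to these patients. The plan does not say so: it is a shock rate for a different group. Let c be the unknown share of events that come to light without a device. Expected events = N × 0.015 × c, and P(no events) = (1 − 0.015c)^N.

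| c (assumed) | N = 200: expected, P(0) | N = 246: expected, P(0) |
|---|---|---|
| 1 | 3.0, 4.9% | 3.7, 2.4% |
| 0.75 | 2.25, 10.4% | 2.8, 6.2% |
| 0.5 | 1.5, 22.2% | 1.8, 15.7% |
| 0.25 | 0.75, 47.2% | 0.9, 39.7% |

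Even with full capture, zero events leaves a one-sided 95% upper bound of 1 − 0.05^(1/N). That is 1.49% at N = 200 and 1.21% at N = 246, close to the planning rate itself.

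**The case against.** The strongest reply is that the plan already keeps most of these things apart. Untreated VT/VF (8.3.3) and other arrhythmias (8.3.5) are limited to WCD recordings, treatments have their own section (8.3.2), and deaths are analysed in 8.3.6. Section 8.3.4 is descriptive and names no groups. Reporting SCA by group is inferred from the general sentence in 2.1. The only event analysis tied explicitly to EF recovery is mortality, which needs no device. All of this stands, and it limits the point to a clarification of the endpoint. It does not remove the conflict between 2.2.1 and 8.3.4, the missing definition of SCA, or the inclusion of device treatments through 3.3. Nothing in 2.1 exempts SCA from by-group reporting.

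A reader might infer three stronger things, none of which the documents support.

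- That nobody records events in recovered patients. Contacts at days 90, 120, 150, 180, 270 and 360 apply to every study patient whether or not the WCD continues (6.2). Table 2 lists SCA at each of them, survival is sought for all (6.4), and cause of death goes to an independent committee (8.3.6).
- That the bias can be put at a given percentage. Any such figure is simply 1 − c, and the documents give no c.
- That section 1.3, which cites a trial finding "a decreased risk of total mortality, although no reduction in arrhythmic events", contradicts the label of the first group. The label describes the day-90 assessment, and 1.3 itself notes that the cited trial excluded reversible cardiomyopathies. Relabelling is optional wording.

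**Conclusion.** The concern holds in a limited form. Ascertainment of non-fatal SCA and VT/VF depends on device status, and device status largely, but not wholly, follows the day-90 group. The two stated windows conflict, and SCA is not defined apart from SCD. A single incidence to end of study, above all one split by the 2.1 groups, would therefore mix risk with detection and treatment.

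This does not mean that the recovered group is bound to look safe. Deaths and recognised arrests are collected for every study patient, and device treatment can make the device groups look safer on deaths. What can be said about size is the 75% and 50% of follow-up without recording under the stated stopping times, and that the expected events are few. The event counts rest on an assumed common rate of 1.5% and on one third recovering by day 90. The conclusion about mixed ascertainment rests on the text alone.

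**What to change.** Reconcile 2.2.1 with 8.3.4 so that the observation window is stated once, and define SCA separately from SCD. Then split the endpoint in 8.3.4.

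1. Report device-detected or device-treated VT/VF, from WCD or ICD, only per patient-time on a device. Apply this in every day-90 group, so that time after refusing a device or stopping the WCD without an ICD is left out of the denominator. Make no comparison with unmonitored time. Recorded wear time (7.1) and ICD placement (6.2.1.2) supply the denominators.
2. Report all-cause death, SCD and clinically attended arrest for all study patients to day 360. Show shock-aborted arrests as a separate line and do not drop them. Dropping them would remove an aborted arrest from the device groups while the same episode counts as a death or attended arrest off device, which reverses the bias.
3. State that device treatment can lower the counts in item 2, so that differences between day-90 groups are not evidence of low arrhythmic risk after EF recovery. Give the source of ascertainment for each event.

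The cost is protocol and SAP wording, with no new data and no change to patient care. The downside is fewer events in each component, and so wider intervals.

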## 4 Study Subject

#### 4.1 Inclusion Criteria

The population for this study will be patients who had an ejection fraction (EF)  $\leq$  35% following hospitalization for newly diagnosed HF, and who have already been using a WCD for 90 days. Prior to 90 days, eligible patients will be enrolled into a registry. Registry patients will be enrolled during the first 30 days of WCD use.

All of the following must be true for enrollment into the registry (day 0 – 90 of WCD use):

- 4.1.1 Patients (≥18 years old) who were prescribed the WCD ≤ 10 days post-discharge after hospitalization for a primary reason of newly diagnosed HF with reduced EF (≤30 days since first HF hospitalization), with ischemic or nonischemic cardiomyopathy, and have used the WCD for no more than 30 days.
- 4.1.2 Patients who had an EF  $\leq$  35% during index hospitalization.

All of the following must be true for enrollment into the study (day  $90 \pm 14$ ):

- 4.1.3 Patients (≥18 years old) who were prescribed the WCD ≤ 10 days post-discharge after hospitalization for a primary reason of newly diagnosed HF with reduced EF (≤30 days since first HF hospitalization), with ischemic or nonischemic cardiomyopathy, and either 1) have already used a WCD for 90 ± 14 days or 2) were enrolled in the registry after 01-March-2019 and received an ICD prior to 90 days of WCD use.
- 4.1.4 Patients who had an EF  $\leq$  35% during index hospitalization. Of note, EF at 90  $\pm$  14 days post-hospitalization does not need to be low to be included in the study.

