## 6 Study Procedures

## 6.1 Subject Recruitment and Screening

### 6.1.1 Subject screening for WCD registry and study

Patients will initially be screened from the prescribed WCD patients and enrolled into the prestudy registry. At 90  $\pm$  14 of WCD use, study subjects will be identified and screened from the clinical site's pre-study registry participants. The sponsor may also assist in the screening process by maintaining a current list of WCD prescribed patients to be screened for the registry by each site. Registry participation is complete when the patient enters the HF Opt study, or ends WCD use.

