6.2.2 Visit post-index hospitalization (day 0 - 30 from WCD start)

- 6.2.2.1 Inclusion/exclusion will be verified.
- 6.2.2.2 Informed Consent for registry will be obtained.
- 6.2.2.3 Clinical history data will be collected, including current Echo and ECG data.
- 6.2.2.4 Medication usage will be collected
- 6.2.2.5 QOL data will be collected (subset of patients only)

The following scheduled visits are for all study patients, regardless of ongoing WCD use, and include:

- 6.2.3 Visit 1 Enrollment (day 90 ± 14 from WCD start)
  - 6.2.3.1 Inclusion/exclusion will be verified.
  - 6.2.3.2 Informed Consent will be obtained.
  - 6.2.3.3 Clinical data will be collected, including current Echo and ECG data.
  - 6.2.3.4 Medication usage will be collected and any adjustments made to achieve GDMT.
  - 6.2.3.5 QOL data will be collected (subset of sites only)

For patients who will be continuing WCD use only:

6.2.3.5 Medical orders and dispensing of the WCD will follow current commercial procedures.

 Spertus and Jones. Development and Validation of a Short Version of the Kansas City Cardiomyopathy Questionnaire. Circ Cardiovasc Qual Outcomes. 2015;8:00-00.

6.2.4	Patient intervi	lews through follow-up phone calls or office visits (days 120 $\pm$ 14 and 150 $\pm$ start)
	6.2.4.1	Clinical data will be collected
	6.2.4.2	Medication changes will be collected
	6.2.4.3	Device information, adverse events, and cardiac event information will be collected as needed
6.2.5	Visit 2 (day 18	30 ± 14 from WCD start)
	6.2.5.1 6.2.5.2	Clinical data will be collected, including current Echo.  Medication changes will be collected.
	6.2.5.3	Device information, adverse events, and cardiac event information will be collected.
	6.2.5.4	If patient has recently ended the study, or WCD use, reasons will be collected.
	6.2.5.5	QOL data will be collected (subset of patients only)
6.2.6	Patient intervi	iew through follow-up phone calls or office visits (day 270 $\pm$ 14 from WCD
	6.2.6.1	Clinical data will be collected.
	6.2.6.2	Medication changes will be collected.
	6.2.6.3	Device information, adverse events, and cardiac event information will be collected.
	6.2.6.4	If patient has recently ended the study, or WCD use, reasons will be collected.
6.2.7	Visit 3 (day 36	60 ± 14 from WCD start)
	6.2.7.1	Clinical data will be collected, including current Echo.
	6.2.7.2	Medication changes will be collected.

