#### 6.3 Unscheduled Visits

Unscheduled visits for registry or study patients may include:

collected.

6.3.1 Resuscitation from SCA event, death, inappropriate shock, and unanticipated end of WCD use or study completion (immediately following notification of occurrence)

6.3.1.1	In the event of a WCD recording that indicates shock, sustained VT/VF >30
	seconds with no shock, or asystole (<10 BPM), sites will be notified from
	ZOLL of the occurrence, and ECG strips will be sent.

- 6.3.1.2 Clinical data will be collected, including any additional EF measurements that were taken at the end of WCD use.
- 6.3.1.3 Device information, adverse events, and cardiac event information will be collected.
- 6.3.1.4 At the end of the study or WCD device use, the reason for discontinuing will be recorded.

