## 6.4 Long-term Clinical Outcome Assessment

Final survival assessment will be 1 year from WCD start of use, ± 14 additional days.

6.4.1 Sites will be asked to determine survival for all patients enrolled in the study through either routine medical records and appointments, or a phone call to the patient.

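### SCA incidence is counted from WCD start, but registry consent can come as late as day 30, so fatal SCA before consent cannot be observed and early fatal incidence is understated if risk time starts at day 0

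*Combined protocol and SAP*

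**What the plan says.** - **Window.** Section 8.3.4 will use descriptive statistics to "analyze the incidence and etiology of SCA from the beginning of LifeVest use to end of study". It names no analysis set, denominator, person-time or censoring rule. Section 8.4 refers the reader elsewhere in the protocol, and 8.6.3 does not deal with delayed entry.
- **A different window.** Objective 2.2.1 reads "Observe the incidence and etiology of SCA and all sustained VT/VF arrhythmias during WCD use".
- **Entry.** Section 4.1: "Registry patients will be enrolled during the first 30 days of WCD use". At the day 0-30 visit in 6.2.2, "Informed Consent for registry will be obtained".
- **Exit from the registry.** Section 6.1.1: "Registry participation is complete when the patient enters the HF Opt study, or ends WCD use". Table 1 schedules no registry data after WCD end.
- **Later follow-up.** Section 6.4: "Sites will be asked to determine survival for all patients enrolled in the study", to one year from WCD start. Sections 3.1.5 and 7.1 keep study patients under follow-up whether they continue the WCD, receive an ICD or have neither.
- **Events after consent.** Section 6.3 covers SCA and death in both groups: "Unscheduled visits for registry or study patients may include".
- **Early ICD recipients.** Under 4.1.3, patients may enter the study if they "were enrolled in the registry after 01-March-2019 and received an ICD prior to 90 days of WCD use".

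**The concern.** The time origin (WCD start) and the start of observation (consent) can be up to 30 days apart. Consent needs a living patient. For everyone enrolled, the days before consent are therefore free of fatal SCA by construction. Counting those days as time at risk adds exposure in which no fatal event could have been recorded.

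A second problem lies at the other end of the window. Registry-only patients leave observation when the WCD ends, while study patients are followed to day 360 in three device states. The reasons for ending the WCD (recovery, an ICD, non-use) may be related to SCA risk. One pooled incidence would then mix populations and device states, with censoring that may be informative.

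At stake is the SCA rate in the first weeks after discharge, which Section 1.1.2 itself describes as high-risk. A rate biased downward by the entry rule would misdescribe the period the device is meant to cover.

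**Working it through.** **The plan's own figures.** The documents give no SCA incidence. The nearest figure is the chance of at least two shock events at a 1.5% rate (Section 8.1.1): 1 − 0.985^n − n × 0.015 × 0.985^(n−1). This is 0.803 at n = 200 (stated as about 80%) and 0.890 at n = 250 (stated as more than 90%, so just short of it). The check shows only that the plan expects few arrhythmic events, so losing a handful could be visible.

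**Inputs**
- Latest entry is day 30 (4.1).
- End of study is 12 months from WCD start (3.1.3), taken as day 360.
- The distribution of entry days is not given. I assume a mean of day 15 (entry spread evenly over days 0-30) and take day 30 for everyone as the extreme.
- The hazard of fatal SCA is assumed to be a constant λ, small, with full follow-up to day T.

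**Loss of rate.** A patient entering at day e can contribute fatal events only over T − e days, so expected events are about λ(T − e). Dividing by T days gives λ(T − e)/T, a loss of e/T. Dividing by T − e days (delayed entry) gives back λ.

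| Entry day e | Loss, days 0-90 | Loss, days 0-360 |
|---|---|---|
| 15 | 15/90 = 17% | 15/360 = 4% |
| 30 | 30/90 = 33% | 30/360 = 8% |

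The expression is linear in e, so a mean of 15 stands for even entry over days 0-30. A hazard that is higher early makes the loss larger.

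**Illustrative counts.** Assume 90-day mortality m of 2% to 10%. The upper value is taken from the background figure in 1.1.1 (over 10%); the lower is my assumption. Assume also that half of deaths are sudden (1.1.1 says this of cardiovascular deaths; I treat all deaths as cardiovascular) and that the WCD has no effect. Then λ = −ln(1 − m)/90, and with even entry the share dying before consent is 1 − (1 − e^(−30λ))/(30λ), where this e is the exponential constant.
- m = 2%: share 0.34%. Per 1,400 enrolled: 1,400 × 0.0034/0.9966, about 5 deaths, of which about 2 are sudden.
- m = 10%: share 1.74%. Per 1,400 enrolled: 1,400 × 0.0174/0.9826, about 25 deaths, of which about 12 are sudden.
- If all entered at day 30, the share is 1 − e^(−30λ), or 0.67% to 3.45%: about 9 to 50 deaths, of which about 5 to 25 are sudden.

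**Non-fatal SCA before consent.** WCD wear and ECG data are downloaded to the sponsor's database (7.1), and registry baseline data come from chart review (6.2.1.1). An early survivor who later consents could therefore have the event counted. An early death could not. On the other hand, 3.1.5 allows an ICD after an aborted SCA, so some early survivors may stop the WCD and never be enrolled.

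**The case against.** The strongest reply is that the plan states no wrong rule. Section 8.3.4 promises descriptive statistics and does not say that pre-consent days go into a denominator. That is correct: the bias follows only if the analyst uses the origin the section names. But that origin is the only instruction given, and nothing elsewhere provides for delayed entry.

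Other parts of the reply stand and limit the point:
- **Size.** A reader might apply the 17% to 33% to the whole window. Section 8.3.4 runs to end of study, where the loss is about 4% to 8% with full follow-up.
- **Total SCA.** The endpoint covers all SCA. Section 1.4.1 reports 94% survival to conscious emergency-room arrival, so most treated events in wearers may be non-fatal. If these are retrieved, the loss in total SCA is smaller than in fatal SCA.
- **Survival after SCA.** A reader might infer that it is bound to look too good. That holds if pre-consent survivors are counted. If early survivors also go unenrolled, the direction is not established.
- **Unequal follow-up.** This is ordinary censoring and not in itself an error. The concern is whether leaving at WCD end is informative. The study-entry route for early ICD recipients narrows that loss, but only for those enrolled in the registry after the stated date.
- **Objective 2.2.1.** If its window is the intended one, ending observation at WCD end is by design and most of the mixed-exposure concern falls away. The two sections still disagree.

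**Conclusion.** The point holds in a limited form. Fatal SCA between WCD start and registry consent cannot be observed, and counting risk time from the origin in 8.3.4 understates fatal SCA incidence. The loss is about 17% to 33% over days 0-90 and about 4% to 8% over days 0-360. These figures rest on a constant hazard, full follow-up and assumed entry days (mean 15, or all at 30). Front-loaded risk would increase them.

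The documents do not support the wider reading that all deaths before day 90 are missed: Section 6.3 collects SCA and death in registry patients after consent. Nor do they show how far censoring at WCD end distorts the later rate, or in which direction. The conflict between 2.2.1 and 8.3.4 is plain from the text. The endpoint is secondary and descriptive, so no power or alpha figure is affected; this should be corrected, but it does not threaten the primary analysis.

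**What to change.** 1. Reconcile 2.2.1 with 8.3.4 and state one SCA window and one analysis set.
2. Start at-risk time at registry consent (delayed entry), with days still counted from WCD start. Leave pre-consent SCAs out of the rate numerator and list them separately.
3. Censor registry-only patients at WCD end, and tabulate the reasons for ending so that readers can judge whether the censoring is informative.
4. Report SCA per 100 patient-months separately for days 0-90 and 90-360, and by device state at the time (WCD, ICD, none). The rate on WCD also answers 2.2.1 as worded.
5. Show the patient-months observed in days 0-30. If risk falls over time, a pooled 0-90 day rate still leans toward the later, better-observed days.

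The cost is SAP wording and slightly lower precision in the early period. Consent, end of WCD use and ICD implantation are already recorded (Tables 1 and 2), and visits are timed from WCD start. No study procedure changes.
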